6.11.4.4 Independent Data Monitoring Committee

An independent unblinded DMC will review the safety data during the study conduct. The DMC Charter will describe the data review process and its frequency.

6.11.4.5 Recording Adverse Events

All AEs and SAEs, whether spontaneously reported by the subject or elicited or noted by study staff, will be recorded in the subject’s medical record and on the appropriate AE eCRF page. In addition, the SAE Report Form must record each SAE.

All AEs should be recorded using the words of the subject (verbatim term) to describe the AE, with two exceptions: if the verbatim term is vague or ambiguous (e.g., cramps), the study staff should try to obtain clarification by asking a follow-up question (e.g., What kind of cramps?) and record the words the subject used to clarify the event (e.g., menstrual cramps, calf muscle cramps).

If the subject reports a group of symptoms and the Investigator is comfortable with a unifying diagnosis, the diagnosis should be recorded (e.g., rhinopharyngitis instead of runny nose, cough, sore throat and sneezing). If a diagnosis is recorded, signs and symptoms need not be recorded separately. If the Investigator is unable to report a diagnosis, symptoms should be recorded on the AE eCRF.

The following information should be captured for each AE: date of onset and resolution, outcome, severity, seriousness, relationship to the study drug, action taken with the study drug and treatments administered. Any treatment administered as a result of an AE should be recorded on the concomitant medication eCRF.

6.11.5 *Clinical Laboratory Abnormalities and Other Abnormal Assessments*

Clinically significant abnormal laboratory tests, vital signs, ECG abnormalities, and physical examination findings before the administration of the first dose of study drug should not be reported as AEs, but rather, as medical history, unless they are expected findings from medical history that has already been reported (e.g., elevated phosphate in a patient with a history of hyperparathyroidism).

Clinically significant new or clinically significantly worsening abnormal laboratory findings (e.g., serum chemistry, hematology, and urinalysis) or other abnormal assessments (e.g., ECGs, vital signs) after the first dose of study drug must be recorded as AEs or SAEs.

Abnormalities resulting in study drug discontinuation, those associated with clinical signs or symptoms, or requiring treatment should be reported as AEs.

6.11.6 *Serious Adverse Events Reporting*

The Investigator has the obligation to report each SAE to Tricida's designee, [REDACTED] [REDACTED], within **24 hours** of knowledge of the occurrence. This includes events that occur during the Follow-up Period. Additionally, if the Investigator learns of any SAE that occurred after the Follow-up Period for which there is a reasonable possibility of relatedness to the investigational drug, that event must be reported within **24 hours**.

SAEs must be reported by entering the SAE information into the SAE CRF in the electronic data capture (EDC) system. [REDACTED] Drug Safety will receive notification of the initial SAE via an e-mail alert generated from the EDC system.

If the event meets seriousness criteria and it is not possible to access the EDC, SAE reporting via a paper form will be required. Submit SAE information via paper form as described in Figure 3. The SAE information must be entered onto the SAE eCRF as soon as the EDC system becomes accessible. All SAEs should be followed until they are resolved or stabilized and all relevant information is compiled. Follow-up information must be handled in the same way and reported within the same time frame as the initial report.

Figure 3 Serious Adverse Event Reporting Instructions if EDC System is Not Available

SERIOUS ADVERSE EVENT REPORTING INSTRUCTIONS

Drug Safety
[REDACTED]
E-mail: [REDACTED]
Fax number: [REDACTED] (for sites in Europe)
Fax number: [REDACTED] (for sites in the US)

Scan and e-mail the SAE form and any supporting documentation to [REDACTED] within 24 hours of becoming aware of the event. Fax number should be used if e-mail service is not available.

Cause of death is required whenever known. If an autopsy was performed, an autopsy report should be provided.

The electronic SAE Form will be completed with the following information at a minimum:

- SAE term
- Date of onset
- Date of resolution (when medically applicable)
- Outcome
- Action taken for the SAE
- Concomitant medications
- Relevant medical history
- Criteria of seriousness (see [Section 6.11.2](#))
- Study drug name, or code if unblinded, and treatment start date
- Severity of the event
- Causality assessment

Additional information must be provided when available including any relevant records (e.g., Hospital Discharge Summary, Autopsy Report/Death Certificate, diagnostic study reports, etc.). Any supporting information provided should not reveal a subject's identity beyond the agreed study identifier. The Investigator should ensure that information reported is accurate and consistent.

Isolated decline in blood bicarbonate or blood pH, even if assessed as clinically significant by the Investigator, will not be captured as an AE for the purpose of this protocol.

All AEs will be evaluated on a regular basis by the Medical Monitor to monitor safety in the study population.

6.11.6.1 SAE Expedited Reporting

For each AE assessed by either the Investigator or Tricida to be serious, Tricida will determine (1) if the event was unexpected (i.e., the nature or severity is not expected from the information provided in the Investigator's Brochure) and (2) if the event was a suspected adverse reaction. If the event is determined to be a serious, unexpected suspected adverse reaction (SUSAR), Tricida will comply with country-specific regulatory requirements relating to safety reporting to the regulatory authority and Investigators. The Investigator is responsible for notifying his/her respective IRB/IEC.

6.11.6.2 Unblinding Treatment Allocation

Generally, Tricida should only report SUSARs for which the treatment allocation of the subject is unblinded to the pertinent regulatory authorities. Investigators should only receive blinded information unless unblinded information is judged necessary for safety reasons.

When an event may be a SUSAR, the blind should be broken only for that specific subject. The blind should be maintained for individuals responsible for the ongoing conduct of the study (e.g., management, monitors and investigators) and those responsible for data analysis and interpretation of results at the conclusion of the study (e.g., biometrics personnel).

Unblinded information should only be accessible to those who need to be involved in the safety reporting to pertinent regulatory authorities, IECs/IRBs, and the Medical Monitor (i.e., the individual performing ongoing safety evaluations during the study).

6.12 **Procedures for Reporting Pregnancy Exposure and Birth Events**

Should a female subject become pregnant or be suspected of being pregnant while participating in this study, the study drug will be permanently discontinued, and the event must be reported to Tricida's designee, [REDACTED] on the Pregnancy Notification Form within **24 hours** of receipt of information by the study staff.

The Investigator is also responsible for following up the pregnancy at 3 monthly intervals until delivery or termination. Pregnancies should initially be reported in the Pregnancy Notification Form and sent by e-mail to the following address: [REDACTED]

When the outcome of the pregnancy is known, study staff will complete the Pregnancy Outcome Form and e-mail it to the following address: [REDACTED].

While pregnancy is not considered an AE or SAE, any pregnancy complication should be recorded as AEs or SAEs (if applicable). Fatalities, elective or spontaneous abortions, and congenital abnormalities/birth defects must be reported as SAEs.

7 STUDY ACTIVITIES

A complete schedule of study events is presented in Appendix 1. See Table 2 for a description of the analytes measured in each laboratory panel.

7.1 Screening 1 Visit (Week -2)

The Screening 1 Visit will occur within 2 weeks of the Baseline Visit. Subjects should present to the clinic in a fasted state (except water) to ensure that they will be fasted for at least 4 hours prior to blood draws during the visit. The following procedures will be performed:

- Obtain informed consent (must be done prior to any of the following procedures including asking subjects to discontinue any prohibited medications)
- Assign a unique subject identification number using the IRT system
- Evaluate eligibility (inclusion/exclusion criteria)
- Record demographic data (including sex, age, race, and ethnicity) and medical history
- Record all prescription and non-prescription medications taken within 28 days
- Collect vital signs (blood pressure [in triplicate], heart rate, temperature, and respiratory rate [in triplicate])
- Record body weight and height
- Draw fasting blood for the following assessments at local laboratory: i-STAT bicarbonate, enzymatic serum bicarbonate assay or venous blood gas bicarbonate assay, coagulation (for subjects receiving vitamin K antagonists or factor Xa inhibitors only)
- Draw fasting blood for the following assessments at central laboratory: serum chemistry panel, hematology panel, hemoglobin A1c, serum pregnancy test (for women of childbearing potential only)
- Obtain urine for spot urine and urinalysis assessments at central laboratory
- Record AEs

7.2 Screening 2 Visit (Week -1)

Subjects who meet eligibility criteria based on the results of the Screening 1 Visit will return for confirmatory bicarbonate and eGFR measurements at the Screening 2 Visit. Screening 1 and Screening 2 Visits must be at least 5 days apart.

- Evaluate eligibility (blood bicarbonate, eGFR, systolic blood pressure)
- Record prior medications
- Collect vital signs (blood pressure [in triplicate], heart rate, temperature, and respiratory rate [in triplicate])

- Perform a complete physical examination
- Train subject on the repeated chair stand test without collecting the data
- Draw fasting blood for the following assessments at local laboratory: i-STAT bicarbonate, enzymatic assay serum bicarbonate or venous blood gas bicarbonate assay
- Draw fasting blood for assessment of serum chemistry panel at central laboratory
- Provide instructions on collecting 24-hour urine sample starting one day prior to the Baseline Visit and dispense necessary supplies
- Record AEs

7.3 Laboratory Re-Testing and Subject Re-Screening

The Investigator may repeat a failed Screening blood or urine laboratory assessment once per analyte during the Screening Period (including Screening 2 and Baseline Visits) if he/she feels the original result was unexpected (e.g., due to a lab error, etc.). When Screening laboratory values required for study eligibility are repeated, eligibility should be determined based on the most recent value.

If a central laboratory eGFR value from Screening 2 Visit is not available, eGFR can be calculated using CKD-EPI equation based on onsite serum creatinine measurement at the Baseline Visit to establish subject's eligibility. For eGFR, the most recent creatinine at the Screening 1 Visit and the most recent creatinine from Screening 2 Visit should be used. If a central laboratory eGFR value and a local eGFR value are both available at the time of randomization, the central laboratory value should be used for eligibility determination.

For blood bicarbonate, the most recent value available from each of the three visits (Screening 1, Screening 2, Day 1) should be used for eligibility determination.

Re-screening of subjects who fail to meet eligibility criteria will be allowed provided the Medical Monitor approves, the subject repeats the Informed Consent process and all Screening evaluations are repeated; a new subject identification number will be assigned each time a subject is re-screened.

7.4 Baseline Visit (Day 1)

Following completion of the Screening Period, subjects who meet eligibility criteria based on the results of the Screening 1 and 2 Visits will return to the study site for the Baseline Visit on Day 1 (within 2 weeks of Screening 1 Visit) for confirmatory blood bicarbonate measurement. Subjects must present to the site in a fasted state.

The following procedures will be performed:

- Evaluate eligibility (blood bicarbonate and eGFR)

- Record prior/concomitant medications
- Collect vital signs (blood pressure, heart rate, temperature, and respiratory rate) up to 1 hour prior to administration of the first dose of study drug
- Collect body weight any time prior to administration of the first dose of study drug
- Perform repeated chair stand test
- Collect answers to KDQOL questions
- Record ECG (triplicate) any time prior to administration of study drug
- Draw fasting blood for the following assessments at local laboratory: i-STAT bicarbonate, enzymatic assay serum bicarbonate or venous blood gas bicarbonate assay, coagulation (for subjects receiving vitamin K antagonists or factor Xa inhibitors only)
- Draw fasting blood for the following assessments at central laboratory: serum chemistry panel, hematology panel, and biomarker panel
- Obtain urine sample for urine dipstick pregnancy test (women of childbearing potential only)
- Obtain urine for the following assessments at central laboratory any time prior to administration of first dose of study drug: spot urine, urinalysis, and urine biomarker panel
- Obtain 24-hour urine sample for assessment at central laboratory
- Randomize subject using the IRT system
- Dispense study drug per IRT assignment and drug dosing diary [to be done by the Pharmacist only]
- Instruct subject on study drug dosing and diary completion procedures and supervise administration of the first dose [to be done by the Pharmacist only]
- Record AEs
- Dietary counseling
- Schedule next study visit

7.5 Week 1, Week 2, and Week 10 Visits

The allowed visit window is \pm 1 day for all visits during the Treatment Period. The following procedures and assessments will be performed at the Week 1, Week 2, and Week 10 Visits. Subjects must present to these visits in a fasted state.

- Record concomitant medications
- Collect vital signs (blood pressure, heart rate, temperature, and respiratory rate)

- Draw fasting blood for the following assessments at local laboratory: i-STAT bicarbonate, enzymatic assay serum bicarbonate or venous blood gas bicarbonate assay, coagulation (for subjects receiving vitamin K antagonists or factor Xa inhibitors only)
- Draw fasting blood for assessment of serum chemistry panel at central laboratory
- **At Week 2 Visit only:** record 12-lead ECG
- **At Week 10 Visit only:** provide instructions on collecting 24-hour urine sample starting one day prior to the Week 12 Visit and dispense necessary supplies
- Dispense the study drug per IRT assignment and dosing diary [to be done by the Pharmacist only]
- Collect used and unused study drug containers since the previous visit and corresponding dosing diary, assess dosing compliance and perform drug accountability [to be done by the Pharmacist only]
- Record AEs
- Schedule the next study visit

7.6 Week 4 and Week 8 Visits

The allowed visit window is \pm 1 day for all visits during the Treatment Period. The following procedures and assessments will be performed at the Week 4 and Week 10 Visits. Subjects must present to these visits in a fasted state.

- Record concomitant medications
- Collect vital signs (blood pressure, heart rate, temperature, and respiratory rate)
- Collect body weight
- Perform a complete physical examination
- Draw fasting blood for the following assessments at local laboratory: i-STAT bicarbonate, enzymatic assay serum bicarbonate or venous blood gas bicarbonate assay, coagulation (for subjects receiving vitamin K antagonists or factor Xa inhibitors only)
- Draw fasting blood for assessment of serum chemistry panel at central laboratory
- Dispense the study drug per IRT assignment and dosing diary [to be done by the Pharmacist only]
- Collect used and unused study drug containers since the previous visit and corresponding dosing diary, assess dosing compliance and perform drug accountability [to be done by the Pharmacist only]
- Record AEs
- Schedule the next study visit

7.7 Week 6 Visit

The allowed visit window is \pm 1 day for all visits during the Treatment Period. The following procedures and assessments will be performed at the Week 6 Visit. Subjects must present to this visit in a fasted state.

- Record concomitant medications
- Collect vital signs (blood pressure, heart rate, temperature, and respiratory rate)
- Record 12-lead ECG
- Draw fasting blood for the following assessments at local laboratory: i-STAT bicarbonate, enzymatic assay serum bicarbonate or venous blood gas bicarbonate assay, coagulation (for subjects receiving vitamin K antagonists or factor Xa inhibitors only)
- Draw fasting blood for the following assessments at central laboratory: serum chemistry panel, hematology panel, hemoglobin A1c, and serum pregnancy test (for women of childbearing potential only)
- Obtain urine for the following assessments at central laboratory: spot urine, urinalysis, and urine biomarker panel
- Dispense the study drug per IRT assignment and dosing diary [to be done by the Pharmacist only]
- Collect used and unused study drug containers since the previous visit and corresponding dosing diary, assess dosing compliance and perform drug accountability [to be done by the Pharmacist only]
- Record AEs
- Dietary counseling
- Schedule the next study visit

7.8 Week 12 or Early Termination Visit (ET)

The following assessments will be performed at the Week 12 Visit for subjects who completed the entire Treatment Period or ET Visit for subjects who withdrew from the study early. Subjects must present to this visit in a fasted state. The last dose of study drug should be taken on Day 84 of the study, regardless of the date of the Week 12 visit; however, every effort should be made to conduct the Week 12 visit on Day 85, which is in exactly 12 weeks from Day 1 (Baseline Visit).

- Record concomitant medications
- Collect vital signs (blood pressure [in triplicate], heart rate, temperature, and respiratory rate [in triplicate])
- Collect body weight

- Perform a complete physical examination
- Perform repeated chair stand test
- Collect answers to KDQOL questions
- Record 12-lead ECG (triplicate)
- Draw fasting blood for the following assessments at local laboratory: i-STAT bicarbonate, enzymatic assay serum bicarbonate or venous blood gas bicarbonate assay, coagulation (for subjects receiving vitamin K antagonists or factor Xa inhibitors only)
- Draw fasting blood for the following assessments at central laboratory: serum chemistry panel, hematology panel, hemoglobin A1c, biomarker panel and serum pregnancy test (for women of childbearing potential only)
- Obtain urine for the following assessments at central laboratory: spot urine, urinalysis, and urine biomarker panel
- Obtain 24-hour urine sample for assessment at central laboratory
- Collect used and unused study drug containers since the previous visit and corresponding dosing diary, assess dosing compliance and perform drug accountability [to be done by the Pharmacist only]
- Record AEs
- Dietary counseling
- Schedule the next study visit

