TRC101 or placebo will be administered orally as an aqueous suspension, QD with lunch, for 12 weeks. Concomitant oral medications must be taken at least 4 hours before or after study drug administration. The first dose of study drug will be given at the study site on Day 1 in the morning with food. The last dose of study drug will be taken the day before the Week 12 Visit unless the subject is enrolled in the extension Study TRCA-301E.

MAIN EFFICACY ASSESSMENT:

Efficacy will be assessed by blood bicarbonate values.

SAFETY ASSESSMENTS:

Safety assessments will include AEs, vital signs, physical examination (including body weight), safety laboratory measurements, coagulation (for subjects on vitamin K antagonists or factor Xa inhibitors only), spot urine, urinalysis, and electrocardiograms (ECGs).

ENDPOINTS:

Primary Efficacy:

Having a change from baseline (CFB) in blood bicarbonate ≥ 4 mEq/L or having blood bicarbonate in the normal range (22 to 29 mEq/L) at the end of treatment (Week 12 Visit).

Secondary Efficacy:

CFB in blood bicarbonate at the end of treatment (Week 12 Visit).

Exploratory Efficacy:

1. CFB in the total score of the Kidney Disease and Quality of Life (KDQOL) Question 3 items (daily activities) at the end of treatment (Week 12 Visit).
2. CFB in repeated chair stand test duration at the end of treatment (Week 12 Visit).

Safety:

1. AEs, SAEs and withdrawal of study treatment due to AE.
2. Having met the high bicarbonate dose interruption criterion (confirmed > 30 mEq/L) at any time during the Treatment Period.

STATISTICAL ANALYSES:

This is a double-blind, placebo-controlled, parallel-design, 2-arm, study. Subjects will be randomized in a 4:3 ratio into one of the two arms (6 g TRC101 or placebo administered QD with lunch). Randomization will be stratified by baseline blood bicarbonate (≤ 18 mEq/L vs. > 18 mEq/L) and screening eGFR (< 30 mL/min/1.73m² vs. ≥ 30 mL/min/1.73m²), which represents an average of two eGFR values obtained at Screening 1 and Screening 2 Visits.

Two populations will be analyzed in this study:

1. Modified intent-to-treat (MITT) analysis set: All randomized subjects who had baseline and at least one post-baseline bicarbonate values.
2. Safety analysis set: All subjects who received any amount of study drug (TRC101 or placebo).

Frequencies and percentages will be presented for the categorical variables and descriptive statistics will be presented for continuous variables.

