Subjects will record the timing of study drug dosing in a dosing diary. Subjects will be instructed to take any oral concomitant treatment at least 4 hours before or after study drug administration. Subjects will be instructed to bring the completed dosing diary with them to each visit to the study site.

The last dose of study drug will be taken the day before the Week 12 Visit (subjects who continue into the extension Study TRCA-301E will continue study drug dosing per the extension study protocol).

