5.5 Selection and Timing of Dose for Each Subject

Subjects will be randomly assigned by the IRT system to one of the available treatment regimens at the Baseline Visit. The dose of study drug may be uptitrated at or after the Week 4 Visit and throughout the Treatment Period until Week 11 (77 days after the first dose of study drug) for blood bicarbonate levels (refer to [Appendix 2](#)). Study drug will be administered as an oral suspension in water with lunch, QD from the Baseline Visit through 1 day prior to the Week 12 Visit. If a dose of study drug is adjusted, the subject will start the new dose at lunch time on the titration day.

Dosing times for study drug will be collected by the subject on the dosing diary and recorded on the eCRF.

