13 APPENDICES

Appendix 1: Schedule of Events

Study Activity	Period		Screening		Treatment							Follow-up		UNS Visit [v]
	Visit Name		S1	S2	D1	W1	W2	W4	W6	W8	W10	W12 [a]	F1	F2
	Timing		Week -2 [b]	Week -1 [c]	Day 1	Week 1	Week 2	Week 4	Week 6	Week 8	Week 10	Week 12	Week 13	Week 14
Informed Consent		X												
Subject ID Number Assignment in IRT		X												
Eligibility Criteria		X	X	X										
Demographics and Medical History		X												
Prior/Concomitant Medications [d]		X	X	X [t]	X	X	X	X	X	X	X	X	X	X
Vital Signs [e]		X	X	X [t]	X	X	X	X	X	X	X	X	X	X
Body Weight and Height [f]		X [f]		X [t]			X		X		X		X	X
Physical Exam [g]			X				X		X		X		X	
Repeated Chair Stand Test			X [u]	X								X		
KDQOL				X								X		
ECG [h]				X [t]		X		X				X		X
Fasting i-STAT Bicarbonate [i]	L	L	L [t]	L	L	L	L	L	L	L	L	L	L	L
Fasting Blood Bicarbonate (Enzymatic Serum or Venous Blood Gas Assay) [j]	L	L	L [t]	L	L	L	L	L	L	L	L	L	L	L
Coagulation [k]	L		L [t]	L	L	L	L	L	L	L	L	L	L	L
Fasting Serum Chemistry	C	C [l]	C [t]	C	C	C	C	C	C	C	C	C	C	C
Hematology	C		C [t]				C			C		C		C
Hemoglobin A1c	C						C			C		C		
Pregnancy Test [m]	C		L [t]				C			C		C		
Biomarkers (Blood and Urine) [n]			C [t]							C		C		
Urinalysis and Spot Urine Tests	C		C [t]				C			C		C		C
Training on 24-Hour Urine Collection and Dispensing Supplies			X							X				
24-Hour Urine Collection [o]				C [t]							C			
Randomization in IRT			X [t]											
Dispensation of Study Drug and Dosing Diary [p, q, r, s]				X	X	X	X	X	X	X				X
Onsite Study Drug Dosing [q]				X										
Study Drug Dosing Compliance and Accountability [r, s]					X	X	X	X	X	X	X	X		X
Adverse Event Collection	X	X	X	X	X	X	X	X	X	X	X	X	X	X
Dietary Counseling			X					X			X			

Notes: (1) All blood draws for bicarbonate measurements must be done with subjects in a fasted state (at least 4 hours, except water). (2) Weekly visits should be targeted to occur on the same day of the week as Day 1 (e.g., always on Wednesday). Allowed visit windows are \pm 1 day for all study visits during the Treatment and Follow-up Periods.

Abbreviations: C = central laboratory assessment; ECG = electrocardiogram; eGFR = estimated glomerular filtration rate; HbA1c = hemoglobin A1c; ID = identification; KDQOL = kidney disease quality of life; L = local laboratory assessment; UNS = unscheduled.

- ^a Subjects who terminate the study early are required to undergo an Early Termination Visit with all Week 12 Visit procedures to be performed.

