- ^p Dispense study drug per IRT instructions and provide the dosing diary. Instruct subject to take study drug with lunch, at least 4 hours apart from all oral concomitant medications.
- ^q Administer the first dose of study drug on the morning of Day 1, with a snack, while the subject is at the site.
- ^r Instruct the subject to bring the dosing diary to each visit. Review dosing diary vs. study drug supplies and assess dosing compliance. Record dosing diary information at each visit in eCRF. Collect the dosing diary at the Week 12 or at the ET Visit.
- ^s Instruct subject to bring all used and unused study drug to each visit. Collect all used and unused study drug at the Week 12 Visit or at the ET Visit.
- ^t Procedure to be performed prior to administration of the first dose of study drug.
- ^u Train the subjects on repeated chair stand test at the Screening 2 Visit. No eCRF data will be collected.
- ^v Possible procedures during the unscheduled visit are listed. The actual procedures should be determined by the Investigator based on the reason for the unscheduled visit. In all cases, reason for the visit and recording of adverse events and concomitant medications should be done.

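### Protocol 7.8 fixes the last dose at Day 84 whatever the Week 12 visit date, contradicting the synopsis, 5.2 and 5.5; a Day 86 primary sample can then follow one omitted dose, with a small, conservative effect

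*Protocol*

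**What the plan says.** Protocol 7.8 states: "The last dose of study drug should be taken on Day 84 of the study, regardless of the date of the Week 12 visit". It continues: "however, every effort should be made to conduct the Week 12 visit on Day 85".

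Three other places give a different rule:

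- Synopsis, dosage forms: "The last dose of study drug will be taken the day before the Week 12 Visit unless the subject is enrolled in the extension" study.
- Section 5.2: "The last dose of study drug will be taken the day before the Week 12 Visit", with subjects entering TRCA-301E continuing under the extension protocol.
- Section 5.5: "QD from the Baseline Visit through 1 day prior to the Week 12 Visit", with no exception stated.

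Appendix 1 sets the visit window at plus or minus "1 day for all study visits during the Treatment and Follow-up Periods", so a Week 12 visit on Day 84, 85 or 86 is compliant.

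Section 5.5 also says: "Dosing times for study drug will be collected by the subject on the dosing diary and recorded on the eCRF". SAP 13.3 uses first and last dose dates for duration of exposure and lists the diary. It does not derive the time from last dose to the Week 12 sample. SAP Table 2 assigns bicarbonate values from Days 79 to 90 to Week 12.

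**The concern.** The primary endpoint is read from a single Week 12 bicarbonate value, and time since the last dose affects that value. Protocol 1.4.1.2 reports that in Study TRCA-101 bicarbonate fell within 2 days of stopping and was near baseline within 9 days. Section 3.2.2 says that most of the effect is gone in about a week.

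Under 7.8, a subject seen one day late is sampled after a missed daily dose by instruction, not by non-adherence. Sites that read different sections would dose subjects differently before the same sample. Any loss falls almost wholly on TRC101, since stopping placebo changes little. What is exposed is the effect estimate and, more directly, the second primary test, which compares the TRC101 arm alone with a fixed 35% and so has no placebo arm to absorb a shift.

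**Working it through.** **1. Day arithmetic.** Day 1 + 7 × 12 = Day 85, as 7.8 states. For a visit on day V, the last dose is Day 84 under 7.8 and Day V − 1 under the other sections. Doses omitted before the sample under 7.8 = max(0, (V − 1) − 84).

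| Visit day | Last dose, 7.8 | Last dose, synopsis/5.2/5.5 | Omitted before sample under 7.8 |
|---|---|---|---|
| 84 | 84 | 83 | 0 |
| 85 | 84 | 84 | 0 |
| 86 | 84 | 85 | 1 |

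Assuming a noon dose and a 9 am fasted draw, the time since last dose on Day 86 is about 45 hours under 7.8, against 21 hours under the other rule.

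**2. Day 84.** The rules differ on paper, but a fasted morning draw precedes lunch and follows the Day 83 dose under either rule. The dose that 7.8 schedules for that lunchtime normally cannot be taken, because of this instruction in Appendix 1: "Collect all used and unused study drug at the Week 12 Visit or at the ET Visit". That is an administrative oddity with no effect on the endpoint.

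**3. The plan's own power figures.** SAP 8.1 gives over 99% for Fisher's test, and roughly 90% for a lower limit of at least 35% at 50% response with 5% missing.

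- Fisher, exact, 120 v 90, 50% v 10%: above 99.9%.
- 35% test: n = 0.95 × 120 = 114. The Clopper-Pearson lower limit is 34.6% with 50 responders and 35.4% with 51, so 51 are needed. P(X ≥ 51) for X ~ Bin(114, 0.50) = 88.8%.

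Both agree with the SAP.

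**4. Effect of late samples (illustration).**

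- From SAP 8.2: SD 3.0 and placebo change 0.25.
- Assumed: baseline uniform on 15 to 20, and mean TRC101 change m = 3.60 one day after the last dose, which gives 50% response under the SAP 14.1.1 rule.
- At 2 days the mean change is 0.25 + s(m − 0.25), where s is the share of the effect remaining relative to day 1.
- If a fraction q of TRC101 samples is late, response is p = (1 − q)p₀ + q·p₁, and power is P(X ≥ 51) for X ~ Bin(114, p).

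| Assumed decay | s | p₁ | Power, q = 5% | q = 10% | q = 20% |
|---|---|---|---|---|---|
| Exponential, half left at 7 days | 0.891 | 45.3% | 87.9% | 86.8% | 84.5% |
| Linear to zero at 9 days | 0.875 | 44.6% | 87.7% | 86.5% | 83.8% |
| Exponential, 10% left at 9 days | 0.750 | 39.2% | 86.5% | 83.8% | 77.6% |
| Exponential, 5% left at 9 days | 0.688 | 36.7% | 85.9% | 82.5% | 74.1% |

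**5. Sensitivity to the true response.**

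- At 55% response (m = 3.99), power is 98.9% with none late and 97.5-98.5% with 10% late.
- At the SAP 8.2 mean change of 4.25, the same model gives about 58% response, 99.9% power with none late and 99.6-99.8% with 10% late.

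**6. Other analyses.** Exact Fisher power for 114 v 85 at 45% v 10% is 99.99%. The SAP's expected Week 12 mean difference of 4.25 − 0.25 = 4.00, with 10% of TRC101 samples late, becomes 4.00 × [1 − 0.10(1 − s)] = 3.88 to 3.96.

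**The case against.** The strongest reply is that the exposure is narrow. Section 7.8 itself asks sites to aim for Day 85, where all the rules agree. Day 84 is harmless. Only a Day 86 visit at a site that follows 7.8 rather than 5.2 or 5.5 loses a dose. Rollover subjects are exempted in the synopsis and 5.2, and their dosing around the visit depends partly on an extension protocol not available here. The visible power loss needs response at the bottom of the planning range, an assumed late share and an assumed decay. The two faster decays imply losses of 0.84 and 1.05 mEq/L from one missed dose, which may be too steep. All of this stands, and it limits the size of the point. It does not remove the contradiction: the Day 85 target is best effort, the window still permits Day 86, and the 7.8 sentence is written to apply on off-target days.

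A reader might infer more than the documents support:

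- *That the treatment comparison is in danger.* Fisher power stays above 99.9% in the case checked, and the bias runs against the drug.
- *That every Day 86 sample follows a missed dose.* That happens only where 7.8 is followed.
- *That the SAP window invites samples 6 days off drug.* A Day 90 sample after a Day 84 dose is possible, but the visit would already be a protocol deviation.
- *That the power figures are bounds.* They are illustrations; the late share is unknown and the decay data come from 2 weeks of in-unit dosing.

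**Conclusion.** The point holds as an internal contradiction with a small effect. Section 7.8 is wrong as written: it conflicts with the synopsis, 5.2 and 5.5 on every compliant visit day except Day 85, and on Day 86 it places one omitted dose before the primary-endpoint sample. The resulting bias lowers TRC101 response, so it is conservative.

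The 35% test loses a few points of power only if true response is near 50% and a material share of visits fall on Day 86: from 88.8% to about 82-87% with 10% late. At 55% response power stays about 98%. These figures rest on the assumed baseline distribution, decay curves and late share in the working. Confidence is high on the contradiction and its day arithmetic, and low on the size of the loss.

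**What to change.** In Protocol 7.8, replace the Day 84 sentence with: *The last dose is taken the day before the actual Week 12 Visit, except for subjects continuing into TRCA-301E.* Keep the Day 85 target. State the same exception in 5.5.

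Dispense enough at Week 10 to cover a Day 86 visit. Assuming whole cartons of 8 packets (Protocol 5.1.1) sized to last through Day 84, a Day 85 dose is already left over in 8 of the 9 combinations of Week 10 visit day (70, 71 or 72) and 1, 2 or 3 packets a day. The exception is 3 packets a day from Day 72: 13 days × 3 = 39 of 40 packets, leaving 1 when 3 are needed. One more carton covers it. The IRT sets actual quantities, so this should be checked there.

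SAP 11.6 already counts 217 randomised subjects, so the protocol change may come too late. If visits are complete, derive the days from last dose to the Week 12 i-STAT sample from the dosing data already on the eCRF, and tabulate them by arm. That costs one derived variable and one table.

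Leave the primary analysis and the Day 79 to 90 window unchanged. A re-analysis that sets aside late samples is not needed: it would select on events after randomisation, and the likely bias is small and conservative.
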